Hypersensitivity Reactions (HSR)	
Hypersensitivity reactions have been reported as uncommon occurrences with integrase inhibitors, including the closely related compound dolutegravir, and were characterized by rash, constitutional findings, and sometimes, organ dysfunction, including liver injury.
 
While there have been no clinical cases of hypersensitivity to CAB, there is a theoretical risk of systemic or severe hypersensitivity reactions with or without hepatic symptoms associated with use of IM CAB. The long exposures anticipated after IM CAB injection may complicate the management of a drug hypersensitivity reaction, were it to occur.
	
 
• The risk of developing a hypersensitivity reaction post administration of IM CAB will be minimized by the use of a 4-week oral lead-in of oral CAB to determine individual safety and tolerability prior to the introduction of IM CAB.
 
• Clinical assessments, laboratory tests (including liver transaminases) and vital signs will be performed throughout this study (refer to Time & Events Table, Section 7.1). Results from these assessments may aid early detection of HSR.
 
• Oral CAB will be withdrawn immediately for cases with suspected HSR during the oral CAB lead-in phase and would not proceed to the injection phase. Participants in the injection phase would not receive further injections. During oral and IM CAB treatment, any HSR reactions that occur would be managed supportively.
 

Development of Resistance following	Residual concentrations of CAB would remain in the systemic	
 
• Alternative oral HAART regimens will be prescribed within
 

Potential Risk of Clinical Significance	Summary of Data/Rationale for Risk	Mitigation Strategy

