**Participants must be discontinued from the study for any of the following reasons:**

- Participants who are not eligible to continue into the Maintenance Phase.
- Participants who are not eligible, or do not wish to continue on to the Extension Phase.
- Virologic withdrawal criteria as specified in Section 5.5.4 are met;
- For participants in the current ART arm during the Maintenance Phase, plasma HIV-1 RNA  $\geq 50$  c/mL at Week 48 with a confirmatory retest;
- Participant requires substitution or dose modification of current ART;
- Participant requires substitution or dose reduction of CAB LA or RPV LA (oral bridging supply and potential for a second loading dose may be permissible following discussion with the Medical Monitor).
- Liver toxicity where stopping criteria are met and no compelling alternate cause is identified (see Section 5.5.1);
- Renal toxicity are met and no compelling alternate cause is identified;
- QT interval (QTc) interval  $> 550$  msec from three or more tracings separated by at least 5 minutes and considered causally related to IP.
- Grade 4 clinical AE considered causally related to study drug;
- Participant has a Grade 3 or higher rash or Grade 2 rash with evidence of systemic involvement and no compelling alternative cause is identified
- Pregnancy (intrauterine), regardless of termination status of pregnancy.
- Participant withdrew consent

Efficacy data for participants withdrawing from the study will be considered evaluable up to the point at which they are withdrawn using the same criteria for evaluability as for participants who complete the study.

Safety data for all participants who receive any amount of study drug, including participants who withdraw from the study, will be included in evaluations of safety.

If a participant is prematurely or permanently withdrawn from the study, the procedures described in the Time and Events Table for the in-clinic Withdrawal visit are to be performed. An in-clinic Follow-Up visit will be conducted 4 weeks after the last dose of study medication for participants with ongoing AEs, and serious adverse events (SAEs)

related & not related to study drug and also any laboratory abnormalities that are considered to be AEs or potentially harmful to the participant, at the last on-study visit.

All data from the Withdrawal visit will be recorded, as they comprise an essential evaluation that should be done prior to discharging any participant from the study.

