#### **7.4.4.11. Allergic reaction**

Participants may continue study drug for Grade 1 or 2 allergic reactions at the discretion of the Investigator. The participant should be advised to contact the Investigator immediately if there is any worsening of symptoms or if further systemic signs or symptoms develop. Antihistamines, topical corticosteroids, or antipruritic agents may be prescribed.

Participants with Grade  $\geq 3$  allergic reactions that are considered to be possibly or probably related to the study drug should permanently discontinue the CAB LA + RPV LA regimen and the participant should be withdrawn from the study. Participants should be treated as clinically appropriate and followed until resolution of the AE.

Participants in the current ART arm who are receiving ABC as part of their NRTI background regimen should be evaluated for the possibility of a clinically suspected ABC hypersensitivity reaction (HSR) and managed appropriately as outlined in the local prescribing information for ABC.

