## Systemic

PARAMETER	GRADE 1 MILD	GRADE 2 MODERATE	GRADE 3 SEVERE	GRADE 4 POTENTIALLY LIFE- THREATENING
Acute Allergic Reaction	Localized urticaria (wheals) with no medical intervention indicated	Localized urticaria with intervention indicated OR Mild angioedema with no intervention indicated	Generalized urticaria OR Angioedema with intervention indicated OR Symptoms of mild	Acute anaphylaxis OR Life-threatening bronchospasm OR Laryngeal edema
Chills	Symptoms causing no or minimal interference with usual social & functional activities	Symptoms causing greater than minimal interference with usual social & functional activities	Symptoms causing inability to perform usual social & functional activities	NA
Cytokine Release Syndrome	Mild signs and symptoms AND Therapy (i.e., antibody infusion) interruption not indicated	Therapy (i.e., antibody infusion) interruption indicated AND Responds promptly to symptomatic treatment OR Prophylactic medications	Prolonged severe signs and symptoms OR Recurrence of symptoms following initial improvement	Life-threatening consequences (e.g., requiring pressor or ventilator support)
Fatigue or Malaise Report only one	Symptoms causing no or minimal interference with usual social & functional activities	Symptoms causing greater than minimal interference with usual social & functional activities	Symptoms causing inability to perform usual social & functional activities	Incapacitating symptoms of fatigue or malaise causing inability to perform basic self-care functions
Fever (non-axillary temperatures only)	38.0 to < 38.6°C or 100.4 to < 101.5°F	≥ 38.6 to < 39.3°C or ≥ 101.5 to < 102.7°F	≥ 39.3 to < 40.0°C or ≥ 102.7 to < 104.0°F	≥ 40.0°C or ≥ 104.0°F
Pain (not associated with study agent injections and not specified elsewhere) Specify location	Pain causing no or minimal interference with usual social & functional activities	Pain causing greater than minimal interference with usual social & functional activities	Pain causing inability to perform usual social & functional activities	Disabling pain causing inability to perform basic self-care functions OR Hospitalization indicated

PARAMETER	GRADE 1 MILD	GRADE 2 MODERATE	GRADE 3 SEVERE	GRADE 4 POTENTIALLY LIFE-THREATENING

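### Suspected hypersensitivity at lower grades is a stop in Section 4.8.1 but investigator discretion in Section 7.4.4.11, and Section 5.5 carries neither rule as such

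*Protocol*

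**What the plan says.** Four places in the Protocol bear on this point.

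- **Section 4.8.1, Hypersensitivity Reactions row.** HSR with integrase inhibitors is described by reactions that "were characterized by rash, constitutional findings, and sometimes, organ dysfunction, including liver injury". The mitigation is "Oral CAB will be withdrawn immediately for cases with suspected HSR during the oral CAB lead-in phase and would not proceed to the injection phase". For those already injected, "Participants in the injection phase would not receive further injections". Neither sentence sets a grade or asks for a causality judgement beyond suspicion.
- **Section 7.4.4.11, Allergic reaction.** "Participants may continue study drug for Grade 1 or 2 allergic reactions at the discretion of the Investigator". At Grade 3 or above, participants whose reactions are considered "possibly or probably related to the study drug should permanently discontinue the CAB LA + RPV LA regimen" and be withdrawn from the study.
- **Section 5.5, mandatory discontinuation list.** The nearest entry is "Participant has a Grade 3 or higher rash or Grade 2 rash with evidence of systemic involvement and no compelling alternative cause is identified". Related Grade 4 clinical adverse events and the liver stopping criteria of Section 5.5.1 are also listed. Neither suspected HSR nor a Grade 3 allergic reaction has its own line.
- **Appendix 2, Systemic table.** Grade 2 acute allergic reaction is "Localized urticaria with intervention indicated OR Mild angioedema with no intervention indicated".

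**The concern.** The oral lead-in is there to find intolerance before a product that cannot be removed is injected. Section 4.8.1 itself notes that prolonged exposure may complicate management of an HSR, and its resistance row puts residual cabotegravir at more than a year in some subjects. The stop on suspicion is part of the mitigation on which the benefit:risk case rests.

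If the sections that describe day-to-day management do not carry the same stop, two sites facing the same event can act differently and each cite the protocol. The first stake is participant safety. A lesser one is that discontinuation due to adverse events is a secondary endpoint, and part of it would then depend on which section a site had read.

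**Working it through.** No arithmetic applies: no rate, sample size or error probability enters. The check is to take specific presentations and read each section against them.

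**Inputs.** The HSR row of 4.8.1; 5.5 and 5.5.1; 7.4.4.11; 7.4.4.13; Appendix 2 grades for acute allergic reaction and rash; and the pre-injection consultation rules in 4.2.2 and 7.4.4.13. In every case below the investigator suspects HSR to study drug, and where 7.4.4.11 asks for relatedness it is taken as possible or probable.

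| Presentation | 4.8.1 | 7.4.4.11 | Other stops (5.5, 5.5.1, 7.4.4.13) |
|---|---|---|---|
| A. Mild angioedema, no intervention (Grade 2), no rash, normal ALT | Stop | Discretion | None met |
| B. Localized rash (Grade 1) with low-grade fever, normal ALT | Stop | Discretion, if treated as an allergic reaction | None met |
| C. Diffuse rash (Grade 2) with systemic involvement, no compelling other cause | Stop | Discretion by grade alone | 5.5 stops |
| D. Grade 2 or higher rash with an ALT increase | Stop | By grade | 7.4.4.13 stops permanently |
| E. Fever and rash with ALT at least 3 times the upper limit, baseline ALT below that limit | Stop | By grade | 5.5.1 stops, and it names hypersensitivity symptoms |
| F. Angioedema needing intervention (Grade 3), no rash | Stop | Withdraw | No line in 5.5 |
| G. Anaphylaxis (Grade 4), related | Stop | Withdraw | 5.5 stops |

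**Cases C, D, E and G.** Another operative section supplies a stop, so 4.8.1 is matched in practice.

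**Cases A and B.** These are the conflict. 4.8.1 gives a stop, 7.4.4.11 gives discretion, and nothing in 5.5, 5.5.1 or 7.4.4.13 settles it. Case B matters because rash with a constitutional finding fits the description in 4.8.1, which makes organ dysfunction only an occasional feature. The rash-management guidance in 7.4.4.13 is confined to rash without systemic or allergic symptoms, so it does not take over.

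**Case F.** This is a second omission. A withdrawal that 7.4.4.11 already requires is missing from the list of mandatory withdrawals.

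**Consultation before the first injection.** Section 4.2.2 makes the first injections a matter for consultation with the Medical Monitor after a significant safety event on oral treatment. Sections 4.2.2 and 7.4.4.13 require any possibly related rash in the lead-in to be discussed first. A discussion is not the outcome that 4.8.1 states, which is "Oral CAB will be withdrawn immediately for cases with suspected HSR during the oral CAB lead-in phase" and no injection. The rash rule also does not reach angioedema without rash, and neither rule covers events after injections have begun.

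**Abacavir comparison.** The only operative section devoted to HSR, 7.4.4.12, concerns abacavir, and it does state an ungraded stop when HSR cannot be ruled out. Cabotegravir has no operative counterpart.

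**The case against.** The best defence is that the two sections speak of different things. Section 4.8.1 has a systemic or severe syndrome in mind; the Grade 1 and 2 entries in Appendix 2 are localized urticaria and mild angioedema. Section 7.4.4.11 treats abacavir HSR apart from its graded rule and tells participants to report further systemic signs at once. On that reading a localized reaction may continue and a suspected syndrome stops. This explains part of the tension but not all of it. Neither term is defined against the other, 4.8.1 acts on suspicion, and case B fits its description at a low grade.

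Second, 7.4.4.11 permits continuation and does not require it. An investigator who suspects HSR and stops complies with both sections. That stands: the conflict is between a stop and a discretion, not between a stop and an order to continue.

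Third, nothing makes 4.8.1 non-binding; Section 4.8 presents it as the mitigation strategy for this protocol. That is also fair, but it makes the discretion in 7.4.4.11 harder to reconcile.

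A reader might go further and infer that the mandatory list has no hypersensitivity trigger at all, so that the safeguard is not in force. The documents do not support this. Section 5.5 brings in the liver criteria, which name hypersensitivity symptoms; it lists the rash and Grade 4 triggers; 7.4.4.13 adds rash with an ALT increase; and 7.4.4.11 itself withdraws related Grade 3 reactions.

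**Conclusion.** The inconsistency holds in a limited form. For a suspected HSR of lower grade, without systemic Grade 2 rash and without a qualifying ALT rise, Section 4.8.1 states a stop and Section 7.4.4.11 leaves the decision to the investigator, both in the lead-in and during injections. Section 5.5 lists neither that stop nor the Grade 3 allergic-reaction withdrawal. The conclusion assumes that an investigator may reasonably suspect HSR in such a presentation; the text does not exclude it.

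The number affected cannot be derived, because the Protocol gives no event rate. It is likely to be small: Section 4.8.1 reports no clinical cases of hypersensitivity to cabotegravir and calls the risk theoretical. A reader might take 285 randomised plus 285 switching participants as the size of the problem. Those are planned arm sizes, not events, and Section 4.3 expects most participants to move to ATLAS-2M, some directly at Week 52. The point merits correction because it concerns a stopping rule around an irreversible injection, not because many cases are foreseen.

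**What to change.** Reconcile Sections 4.8.1, 5.5, 7.4.4.11 and 7.4.4.13:

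1. Define suspected HSR to study drug and say how it differs from an allergic reaction graded under Appendix 2.
2. State one rule, with its grade and causality conditions, for the oral lead-in and for the injection phase, and say how Medical Monitor consultation relates to it.
3. List that rule in Section 5.5, together with the withdrawal for related Grade 3 or higher allergic reactions that 7.4.4.11 already contains.

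Which rule stands is for the sponsor's clinicians. The cost is an amendment to wording in these sections. The design, sample size and planned analyses do not change.

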#### 4.8.1.1. Other Clinically Relevant Information

Additional details concerning safety observations from clinical studies and for which a causal association has not been established or which are of minimal clinical significance may be found in the Investigator's Brochures (GSK Document number [RH2009/00003/06](#) [CAB IB], [RPV IB](#), 2017).

##### *Adverse Events of Special Interest:*

##### *Seizure*

Three cases of seizures have occurred in the cabotegravir programme cumulatively through 15 May 2016. Two of the cases occurred in HIV uninfected subjects with a prior history of seizure and one case involved a subject in study 200056 with circumstantial and anecdotal evidence of illicit drug use. Overall, there is not convincing evidence that cabotegravir exposure may be causally associated with seizure or with reduction of seizure threshold, due to the low frequency of reports, the confounders present in the cases received to date and lack of any pre-clinical signal or identified plausible mechanism. However seizure and seizure-like events are considered as AEs of special interest for close monitoring in future studies. Subjects with recent history of, or recent treatment for, seizure will be excluded from study participation.

#### **4.8.2. Benefit Assessment**

The antiviral activity against HIV-1 of CAB has been well established through Phase 2a and Phase 2b studies. RPV is an established antiviral agent against HIV-1 in treatment naive patients, with long term durability (>96 weeks in Phase 3 and >240 weeks in Phase IIb).

Participants receiving CAB LA + RPV LA are anticipated to benefit from maintenance of virological suppression using LA agents. Participants randomized to an arm containing CAB LA+ RPV LA will have Q4 weekly dosing without the need to take concomitant daily oral therapy. Adherence in these participants is expected to be improved and will be directly observed during IM injections. Efficacy of the two-drug regimen, as oral agents, has been demonstrated through Week 96 of the ongoing LAI116482 study. Efficacy of the two-drug regimen, as IM agents, has been demonstrated through Week 48 of the ongoing 200056 study. The reduction in ART, and the discontinuation of NRTIs, may offer long term safety and tolerability benefits in these participants.

#### **4.8.3. Overall Benefit:Risk Conclusion**

Taking into account the measures taken to minimize risk to participants participating in this study, the potential risks identified in association with CAB LA and RPV LA and the study as a whole are justified by the anticipated benefits that may be afforded to treatment-experienced patients with HIV-1 infection.

### **5. SELECTION OF STUDY POPULATION AND WITHDRAWAL CRITERIA**

Specific information regarding warnings, precautions, contraindications, adverse events, and other pertinent information on the investigational regimen or other study treatment that may impact participant eligibility is provided in the current Investigator's Brochures (IB) for CAB (GlaxoSmithKline Document Number [RH2009/00003/06](#), 2016) and RPV([RPV IB](#), 2017) and RPV product label.

Deviations from inclusion and exclusion criteria are not allowed because they can potentially jeopardize the scientific integrity of the study, regulatory acceptability or participant safety. Therefore, adherence to the criteria as specified in the protocol is essential.

#### **5.1. Inclusion Criteria**

A participant will be eligible for inclusion in this study only if all of the following criteria apply:

- Be able to understand and comply with protocol requirements, instructions, and restrictions;
- Understand the long term commitment to the study and be likely to complete the study as planned;

- Be considered appropriate candidates for participation in an investigative clinical trial with oral and intramuscularly injectable medications (e.g., no active substance use disorder, acute major organ disease, or planned long-term work assignments out of the country, etc.).

The following are study specific eligibility criteria unless stated otherwise. **In addition to these criteria, Investigators must exercise clinical discretion regarding selection of appropriate study participants, taking into consideration any local treatment practices or guidelines and good clinical practice (GCP). All participants must be considered appropriate candidates for antiretroviral therapy in accordance with local treatment guidelines.**

Laboratory results from the central laboratory services provided by this trial will be used to assess eligibility. In exceptional circumstances only, if a repeat lab is required because a central lab result cannot be generated, local labs can be reviewed and approved by the Medical Monitor for consideration of participant eligibility. A repeat central lab will be submitted concurrently or at the next planned visit.

Source documentation to verify entry criteria must be reviewed by the Principal Investigator or designee prior to randomization. Source documents from other medical facilities must be located/received during the 14 day screening phase (or up to 35 days) and under no circumstances may the participant be randomized in the absence of source documentation.

Participants eligible for enrolment in the study must meet all of the following criteria:

AGE
1. Aged 18 years or older (or $\geq 19$ where required by local regulatory agencies), at the time of signing the informed consent.
TYPE OF PARTICIPANT AND DIAGNOSIS INCLUDING DISEASE SEVERITY

2. Must be on uninterrupted current regimen (either the initial or second ARV regimen) for at least 6 months prior to Screening. Any prior switch, defined as a change of a single drug or multiple drugs simultaneously, must have occurred due to tolerability/safety, access to medications, or convenience/simplification, and must NOT have been done for treatment failure (HIV-1 RNA <math>\geq 400</math> c/mL).
 
Acceptable stable (initial or second) ARV regimens prior to Screening include 2 NRTIs plus:
 
 
• INI with the exception of ABC/DTG/3TC (either the initial or second cART regimen)
 
• NNRTI (either the initial or second cART regimen)
 
• Boosted PI (or atazanavir [ATV] unboosted) (must be either the initial cART regimen or one historical within class switch is permitted due to safety/tolerability)
 
 
The addition, removal, or switch of a drug(s) that has been used to treat HIV

based on antiretroviral properties of the drug constitutes a change in ART with the following limited exceptions:

- Historical changes in formulations of ART drugs or booster drugs will not constitute a change in ART regimen if the data support similar exposures and efficacy, and the change must have been at least 3 months prior to Screening.
  - Historical perinatal use of an NRTI when given in addition to an ongoing HAART will not be considered a change in ART regimen.
  - A change in dosing scheme of the same drug from twice daily to once daily will not be considered a change in ART regimen if data support similar exposures and efficacy.
3. Documented evidence of at least two plasma HIV-1 RNA measurements <50 c/mL in the 12 months prior to Screening: one within the 6 to 12 month window, and one within 6 months prior to Screening;
4. Plasma HIV-1 RNA <50 c/mL at Screening;

#### SEX

5. A female participant is eligible to participate if she is not pregnant (as confirmed by a negative serum human chorionic gonadotrophin (hCG) test at screen and a negative urine hCG test at Randomization), not lactating, and at least one of the following conditions applies:
- a. *Non-reproductive* potential defined as:
- Pre-menopausal females with one of the following:
    - Documented tubal ligation
    - Documented hysteroscopic tubal occlusion procedure with follow-up confirmation of bilateral tubal occlusion
    - Hysterectomy
    - Documented Bilateral Oophorectomy
  - Postmenopausal defined as 12 months of spontaneous amenorrhea [in questionable cases a blood sample with simultaneous follicle stimulating hormone (FSH) and estradiol levels consistent with menopause (refer to laboratory reference ranges for confirmatory levels)]. Females on hormone replacement therapy (HRT) and whose menopausal status is in doubt will be required to use one of the highly effective contraception methods if they wish to continue their HRT during the study. Otherwise, they must discontinue HRT to allow confirmation of post-menopausal status prior to

study enrolment.

**b. Reproductive potential** and agrees to follow one of the options listed in the Modified List of Highly Effective Methods for Avoiding Pregnancy in Females of Reproductive Potential (FRP) (see Section 12.7.1, Appendix 7) from 30 days prior to the first dose of study medication, and until from 30 days prior to the first dose of study medication throughout the study, and for at least 30 days after discontinuation of all oral study medications and for at least 52 weeks after discontinuation of CAB LA and RPV LA.

The investigator is responsible for ensuring that participants understand how to properly use these methods of contraception.

